The sample size calculation is based on the primary outcome of BMD loss at the proximal tibia at 12 months. A set target of at least 50% reduction in percent BMD loss between treatment and control groups is projected. Expected BMD loss is taken from the placebo group of Bauman⁽⁵⁸⁾.

Subjects in this study lost 8% +/- 3% BMD at 3 months and **29% +/- 13%** at 12 months in the proximal tibia. The effect size (difference in mean percent reduction divided by standard deviation) for a 50% reduction in BMD loss is 1.3 at 3 months and 1.1 at 12 months. Assuming 2:1 randomization, two-sample t-test, 80% power and two-sided type-I error rate of 5%, we would need a total sample size of 24 for an effect size of 1.3, 33 for an effect size of 1.1, and 39 for an effect size of 1.0. We plan to enroll 48 subjects to allow for potential attrition. With a dropout rate of 18% we would reach a final sample of 39; a dropout rate of 30% would result in a final sample of 33. The enrollment of 10 subjects/year (total = 40) would still allow an 18% drop out to achieve a final sample of 33.

2. Randomization Method

The randomization schedule will be generated by the TJU Division of Biostatistics. Randomization will use the method of random permuted blocks. The block size will not be disclosed to the investigators. The TJU Division of Biostatistics will prepare a randomization scheme document to be kept by the TJUH Investigational Drug Service (IDS). Once a subject is confirmed to be eligible and the informed consent is completed, the IDS will be alerted to assign a randomization and prepare for the subsequent medication preparation and delivery. A completed randomization assignment log will be returned to Biostatistics so they can monitor randomization and accrual.

3. Management of Study Drug Infusion

The TJUH Investigational Drug Service is a well-established service within the Pharmacy Department that participates in numerous inpatient and outpatient research protocols. The IDS reviews all inpatient investigational drug protocols and assists with patient enrollment (randomization), staff education and maintenance of study records, including protocol budgets. The IDS maintains all investigational drug records in accordance with FDA regulations as well as with the policies and procedures of the Institutional Review Board. The IDS provides the procurement, storage, dispensing and maintenance of records for all investigational drugs.

4. Study Activities and Assessments

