We will compare the treatment and control groups for baseline characteristics using t-tests and Chi-square tests as appropriate. Specifically, we will compare age at injury, baseline FRAX fracture risk, sex and injury level (tetraplegia/paraplegia) distribution. The level of significance for all analyses will be 0.05.

2. Evaluation of Hypotheses

Specific Aim 1: To determine the short and long term effects of zoledronic acid on BMD values of the hip, distal femur, and proximal tibia in patients with acute SCI relative to patients receiving placebo.

The primary hypothesis is that subjects treated with zoledronic acid will have at least a 50% smaller percentage decline in BMD values for the hip, distal femur and proximal tibia at 4 and 12 months post-injury than control subjects.

Analysis: For each of the bone sites to be evaluated, a percent change from baseline ([baseline BMD – follow-up BMD]/baseline BMD) will be modeled using mixed effects linear regression. Fixed effects will be included for treatment assignment, time, treatment by time interaction, and baseline BMD level. A random intercept term will be included to account for correlation among repeated measurements from the same subject. Within this regression model, we will estimate the difference between treatment groups at 4 and 12 months and test for significance of this difference. If the outcome of percent change is not normally distributed, we will apply an appropriate transformation (e.g., log, logit). If the necessary transformation is too complex for interpretation, we will consider using rank-based methods.

Secondary hypothesis 1 is that subjects treated with zoledronic acid will maintain original BMD values for the hip, distal femur and proximal tibia at 4 months and lose no more than 5% at 12 months post-injury.

Analysis: We will estimate the mean percent change at 4 and 12 months for the active treatment group along with associated 95% confidence intervals from the results of the mixed effects regression. BMD values at 4 months will be considered equivalent to those at baseline if the bounds of the confidence interval are within +/-2%. At 12 months, we will test the one-sided null hypothesis that the percentage decline is greater than 5% vs. the alternative that it is less than or equal to 5%.

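### The rule for leaving the percent-change scale checks the outcome instead of the residuals, leaves the check undefined, and falls back on scales that cannot answer the plan's own criteria

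*Combined protocol and SAP*

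**What the plan says.** Section E.2, Specific Aim 1, defines the outcome at each bone site as baseline minus follow-up BMD, divided by baseline, so a loss is positive. This outcome "will be modeled using mixed effects linear regression". The model is described in two sentences: "Fixed effects will be included for treatment assignment, time, treatment by time interaction, and baseline BMD level", and "A random intercept term will be included to account for correlation among repeated measurements from the same subject". No visit-specific variance is mentioned.

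The rule for leaving that model follows: "If the outcome of percent change is not normally distributed, we will apply an appropriate transformation (e.g., log, logit"). Then: "If the necessary transformation is too complex for interpretation, we will consider using rank-based methods". No test, threshold, visit or arm stratum, or residual check is named.

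Three criteria sit on the mean percent-change scale. The primary hypothesis is a decline at least 50% smaller on zoledronic acid (ZA). Under secondary hypothesis 1, "BMD values at 4 months will be considered equivalent to those at baseline if the bounds of the confidence interval are within +/-2" percent, and a one-sided test at 12 months uses a 5% decline. The group means and intervals for secondary hypothesis 1 are to come from the same mixed model.

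The expected values are in D.3, Sample Size Calculations. Placebo patients in the cited pamidronate study "lost 8% +/- 3% BMD at 3 months" and 29% +/- 13% at 12 months at the proximal tibia, and ZA is projected to halve the loss.

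**The concern.** The outcome combines two arms and two visits that the plan expects to differ. Its overall distribution is therefore a mixture and need not be normal even when each component is. The model removes arm, time and interaction effects, so its normality assumption concerns what is left over. Checking the outcome is checking the wrong quantity.

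The rule governs the primary analysis at all three sites, and it leaves the analyst to decide, with data in hand, how to check and where to go next. If the analysis moves to a log, logit or rank scale, the model no longer estimates mean percent change, and the plan gives no replacement for the three criteria stated on that scale.

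**Working it through.** **Inputs from D.3.** Placebo loss: mean 8%, SD 3% at 3 months (used here for the 4-month visit); mean 29%, SD 13% at 12 months. Halving gives ZA means of 4% and 14.5%. The plan's effect size uses one SD for both arms, so the base case does too. Allocation is 2:1, with 33, 39 or 48 patients.

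**The plan's own figures first.** Effect sizes: (8 - 4)/3 = 1.33 and (29 - 14.5)/13 = 1.12, stated as 1.3 and 1.1. Exact t-test power at 2:1 is 0.818 for 24 patients at effect size 1.3, 0.823 for 33 at 1.1, and 0.818 for 39 at 1.0. All three stated totals are reproduced.

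**Assumptions, because the plan is silent.** Shapiro-Wilk test at 5%; within-patient correlation 0.5; no baseline BMD effect; errors exactly normal in every arm-by-visit cell.

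**How often the check fails** (simulated trials, range over 33, 39 and 48 patients):

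| What is checked | Variance setting | Rejected |
|---|---|---|
| Outcome, each visit separately | SD 3 and 13 | about 5% per visit; 8.5-10% at either |
| Outcome, visits pooled | SD 3 and 13 | about 100% |
| Outcome, visits pooled, no treatment effect (39 patients) | SD 3 and 13 | 100% |
| Raw residuals (observation minus arm-by-visit mean), pooled | SD 3 and 13 | 91-99% |
| Residuals standardised within visit and arm | SD 3 and 13 | about 5-6% |
| Outcome, visits pooled | common SD 13 | 6-7% |
| Outcome, visits pooled | common SD 9.4 | 10-17% |
| Outcome, visits pooled | common SD 8 | 17-27% |

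The SD of 9.4 is the root mean square of 3 and 13: sqrt((9 + 169)/2) = 9.4.

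The third and fourth rows identify the cause. Removing the treatment effect leaves the pooled rate at 100%, and moving from outcome to raw residuals barely lowers it. What drives it is the variance ratio between visits, 169/9, or about 19.

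If the ZA SD is also halved (an assumption the plan does not make), the 12-month check alone fails in 58-78% of trials, and at least one visit fails in 82-95%.

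**Log and logit.** Both need a loss above zero. For ZA with equal arm SDs, P(loss <= 0) = Phi(-mean/SD):

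- 4 months: Phi(-4/3) = 0.091. With 26 ZA patients (two thirds of 39), P(at least one) = 1 - 0.909^26 = about 92%.
- 12 months: Phi(-14.5/13) = 0.132. P(at least one) = 1 - 0.868^26 = about 98%.

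If the ZA SD halves with its mean, the cell probabilities are Phi(-4/1.5) = 0.0038 and Phi(-14.5/6.5) = 0.0128. The chance of at least one is then 1 - 0.9962^26 = about 9% and 1 - 0.9872^26 = about 29%. The problem is therefore likely under the plan's single-SD assumption and less likely otherwise. If BMD is maintained at 4 months, as secondary hypothesis 1 expects, the mean loss is near zero and patients with no loss or a gain become common.

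**An input to reconcile.** Section C gives a proximal tibia loss of 42% on placebo at 12 months for the study that D.3 cites for 29%. Using 42% leaves the picture unchanged: pooled with SD 3 and 13, 100%; pooled with common SD 13, 14-18%; 12-month visit alone, about 5-6%.

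**The case against.** The best defence is that the sentence is ordinary shorthand for model checking in a brief grant-style analysis section. It prescribes no formal test and no pooling. The model estimates the difference at 4 and at 12 months, so a visit-by-visit check is at least as natural, and on the plan's inputs that check misfires only about 5% of the time. This stands, and it lowers the severity.

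A reader might infer something stronger: that the rule fires in almost every trial even when the planned model is exactly right, or that a working treatment trips it. The documents support neither. The rate near 100% needs a formal test pooled over visits with SDs of 3% and 13%. A random-intercept model in its usual form has one residual variance, so under those SDs it is not exactly right. With one common SD of 8-13% the pooled rate is 6-27%, and with no treatment effect at all the pooled test still rejects every time. Replacing the outcome by raw residuals would not cure it either.

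It can also be said that a sensible analyst would avoid an undefined logarithm, for example by taking the log of the follow-up to baseline ratio, which exists for every patient. But that is not a transformation of percent change as the plan words it, and it yields a ratio of geometric means. The 50%, +/-2% and 5% criteria would still need restating.

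**Conclusion.** The point holds in a limited form. The trigger names the wrong quantity, and because the check is undefined its false-alarm rate runs from about 5% (by visit) to about 100% (visits pooled) on the same inputs. The upper end reflects unequal variance between visits, which the planned model does not address. These rates rest on the assumed test, the assumed correlation and the 3-month figures standing in for month 4.

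Two consequences do not depend on the simulation. Log and logit of percent loss are undefined for patients with no loss or a gain, and no transformed or rank model directly returns the mean percent change that the plan's criteria use. How often undefined values arise does depend on the ZA SD: about 92% and 98% of trials at the two visits with equal arm SDs, about 9% and 29% if the ZA SD halves.

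This is a cheap improvement that ranks below a must-fix, since a careful analyst could apply the present text without harm.

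**What to change.** Replace the two fallback sentences in E.2, Specific Aim 1, with:

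> Percent change is the primary scale whatever the distribution. The model will allow a separate residual variance at each visit. Model fit will be checked on residuals standardised within visit and arm. A rank-based or permutation analysis will be reported as a sensitivity analysis only.

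One detail of implementation: with only two follow-up visits, an unstructured within-patient covariance is the simplest way to do this. A random intercept with separate residual variances cannot give a covariance above the smaller visit variance. At the plan's SDs and a correlation of 0.5 the covariance is 0.5 x 3 x 13 = 19.5, against 3 x 3 = 9.

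The cost is a few sentences and no extra patients or data. The small downside is that inference stays on the raw scale if residuals are truly skewed, which the sensitivity analysis covers.

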Due to the potency of IV ZA, adverse effects of the agent may occur. The most common side effects of ZA are an acute phase reaction involving fever (15%), myalgias (8%), flu-like illness (7%), headache (6%) and arthralgias (5%)^{61,62}. In rare cases, patients may experience noncardiac chest pain (1/3%). Because infusion of IV ZA can cause an increase in serum creatinine up to 30 days post treatment, the drug should be avoided in persons with creatinine clearance <35 mL/min. An association between atrial fibrillation and IV ZA use was observed in a large study of over 7000 patients⁶². The FDA subsequently conducted an investigation, comparing results of the prior trial to other studies of IV ZA, and concluded that no clear relationship could be identified between bisphosphonate use and atrial fibrillation⁶³. Both oral and IV bisphosphonates have been associated with osteonecrosis of the jaw (ONJ), but further review of the data by the American Dental Association found that incidence of ONJ is rare in post-menopausal women with osteoporosis but more common in those with monthly infusions for cancer treatment⁶⁴. This group recommended no special treatment beyond routine dental care for those using IV ZA for osteoporosis. Finally, several reports of low trauma fractures of the femur have been observed among patients primarily over age 60 who are prescribed chronic bisphosphonate treatment (2.5-8 years)^{61,65}. A recent cohort study of over 1.1 million patients by Dell et al. found that while duration of use of bisphosphonates was correlated with incidence of atypical femur fractures, (particularly beyond 5 years of use), no correlation with age and duration of use was found.⁶⁶ Because our study will involve only a single dose of ZA, we do not anticipate observing the above effect from the drug alone. Based on these new findings, we also believe that individuals ages 61-65 should not be excluded by age alone.

Previous Clinical Trials of Zoledronic Acid

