(5 experimental, 6 control) and 3 incomplete subjects (2 experimental, 1 control). Differences between ZA-treated subjects and controls were 3% for the lumbar spine ($p < .05$); 12% for the total hip ($p < .05$), 5% for the femoral neck (NS), and 11% ($p < .05$) at the greater trochanter 12 months after study drug administration. In the ZA group, BMD at the total hip and greater trochanter were maintained from baseline, but the area of the femoral neck still lost 10% of the original BMD. In both of the above studies, pharmacologic intervention did not occur until 2-3 months post injury, when a notable amount of bone mass is already lost. Furthermore, neither study evaluated BMD at the distal femur and proximal tibia, two high risk areas for sublesional fractures after SCI.

Areal Bone Mineral Density

Since marked sub-lesional bone loss after SCI is found consistently^{5,6}, our study will provide new information on the effectiveness of ZA in preventing bone loss after SCI because it differs from prior studies in the following important aspects:

1. We will administer ZA within 21 days of SCI, when bone resorption is just beginning. This is sooner than the prior studies on ZA in SCI.
2. We will limit enrollment to patients with complete injuries, minimizing potential confounding between ambulatory and non-ambulatory subjects.
3. We will monitor calcium and vitamin D levels periodically throughout the study, with aggressive supplementation of all patients noted to be low, **and** we will supply supplemental calcium and vitamin D to all subjects to prevent anticipated losses in the initial year of injury³⁵.
4. We will evaluate the effect of ZA on BMD at the hip, the distal femur, and proximal tibia.

D. Study Design

This will be a prospective, double-blind, randomized, placebo-controlled trial with a 2:1 ratio of ZA to placebo in 48 persons with complete traumatic SCI.

Study Location and SCI Population

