A. Screening: Post injury days 0-17

- Subjects admitted to the RSCIC with suspected complete SCI will be approached for participation shortly after admission. After providing informed consent, subjects will be screened between 0 and 17 days post injury. The screening will review of the medical record medical/surgical history and physical/neurological examination performed according to ISNCSCI guidelines to ensure an AIS Grade A SCI is present, or post-menopausal) and social or lifestyle factors that could alter ability to participate.
- A serum pregnancy test (for females of child bearing age).
- Standard of Care laboratory tests of kidney (TJUH Basic Metabolic Panel) and liver function (TJUH Hepatic Panel) will be reviewed to ensure the patient does not have a history of chronic liver or kidney failure, unknown to family or subject or not revealed on subject history interview.

- Serum calcium measurement. If initial serum calcium is <7.0 mg/dl, the subject will be given correctional calcium doses in accordance with standard hospital treatment protocol for subjects with critically low calcium levels. The subject may still be able to participate if the calcium level is corrected by the day prior to study drug infusion.
- Serum Vitamin D measurement. Subjects with initial vitamin D levels in the deficient range (<13ng/ml) will not be eligible for participation. If subject's 25-OH vitamin D is between 13 and 20, the subject will be supplemented with high potency oral ergocalciferol 50,000 International Units (IU) per week until retesting occurs at 4 weeks. At the time the screening value is returned, subjects with 25-OH vitamin D levels between 20 and 32 will be started on 2000 IU vitamin D daily and those with levels 32 and higher will be initiated on 1000 IU daily. Supplemental oral calcium of 1200 mg daily will be started on the same day as the vitamin D, except in cases of low values as described above.
- Intact Parathyroid Hormone (iPTH) measurement.

B. Baseline Assessments: Post-injury days 8-21

A Baseline Assessment will be completed between 8 and 21 days post-injury, and include the following:

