- Completion of the World Health Organization (WHO) Fracture Risk Assessment Tool (FRAX)⁷³. The FRAX asks for information about age, date of birth, sex, weight, height, previous fracture history, parental fracture history, smoking, steroid use, history of rheumatoid arthritis, presence of a medical condition related to osteoporosis, alcohol use, and current hip bone mineral density (see data collection forms in Appendix B). All data are then entered into the FRAX website (available through the WHO) to obtain the 10 year probability of a fracture. No personal identifiers are used and no data is saved on the website.
- Collection of blood sample for pre-treatment levels of PINP as measures of bone formation, s-CTX as marker of bone resorption, IL-1 β as a pro-osteoclastogenic factor, CPK (Creatinine Phosphokinase) as a marker of muscle tissue and kidney function, and serum calcium. DXA scan, to be obtained as soon as the subject is medically stable for testing off the intensive/acute care floor (may be done up to 7 days after the infusion of study drug).

C. Study drug infusion: Post injury day 21

Within day 21 post injury, subjects will be administered study drug and assessed as follows:

- Measurement of serum calcium level to ensure therapeutic levels.
- A single IV infusion of ZA 5 mg or a placebo drug with the same dilution and duration of administration (prepared and dispensed by the TJUH IDS).
- The single IV infusion will be administered over a 2 hour period (2.5 mg per hour)
- Supplemental hydration as needed to keep urine output > 2000 cc per day from the day prior to study drug administration until 3 days post-infusion.
- Acetaminophen 650 mg every 4 hours for the 24 hour period following drug administration. This is intended to reduce the frequency and severity of fever or myalgias associated with ZA administration⁶¹.

D. Days 1-7, Post Drug Infusion

- After the first day, acetaminophen will continue to be offered as needed every 4 hours through day 3 post-infusion.
- Supplemental hydration will be continued as needed to keep urine output > 2000 cc per day until 3 days post-infusion
- Subjects will be assessed daily for 3 days, then weekly for one month after study drug administration for known side effects of the drugs, including myalgias, fever, gastrointestinal disturbances, and flu-like symptoms.

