Information on Physical Examinations and Clinical Assessments

Objective Evaluations: To ensure the patient has a complete spinal cord injury (AIS Grade A), investigators will perform a complete neurological exam according to ISNCSCI guidelines as part of initial screening (days 2-17 post injury). A confirmatory exam will be conducted in the 24 hours prior to study drug delivery. At the end of the study when the patient returns for final laboratory tests and DXA scan, a repeat neurological examination will be performed.

Subjective reports: Interviews will be conducted with patients every 2 months during the first year, either in person if testing is scheduled, or by phone between testing sessions. The first phone call will occur 2 months from injury if the subject is not an inpatient or not available for in-person interview. During these interviews, subjects will be asked about any evidence or knowledge of bone fractures since the previous contact. We will obtain information about exercises and standing, (including use of FES), such as how often and average daily duration.

Follow up for Subsequent Years of Grant Cycle

During the subsequent years of the grant cycle, patients will be contacted every 6 months for information on fractures sustained in the prior 6 months. As part of the consent form, we will be requesting permission to receive x-ray reports of any bone fracture experienced and mechanism of injury between years 1 and 4 post injury and collect information on participation in standing, lower extremity exercise and functional electrical stimulation (FES), and current calcium and vitamin D use.

[figure not shown]
Early Termination

Should a subject gain neurological function prior to initial drug administration and no longer have a complete SCI, that potential subject is withdrawn from the study. Should a subject recover neurological function and the SCI be deemed incomplete any time after the study drug has been administered, that participant will continue with all assessments and follow up studies without exception.

5. DXA Scan Analyses

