Specific Aim 3: To determine the safety and tolerability of early administration of intravenous zoledronic acid in persons with acute SCI. We expect to see only minor, transient side effects from zoledronic acid. *To evaluate this we will test the hypotheses that compared to controls, subjects treated with zoledronic acid will have (3a) an increased incidence of myalgias, fever, gastrointestinal disturbances, and flu-like symptoms over the three days after infusion of study drug; (3b) be less likely to participate in physical and occupational therapy during the first week after infusion, and (3c) be less likely to want the treatment again.*

Analysis: For each outcome, we will estimate group-specific rates (proportions) along with exact binomial confidence intervals. Comparisons between groups will be performed using Fisher's exact test.

References Cited

1. National Institute on Disability and Rehabilitation Research. Notice of Final Long-Range Plan for Fiscal Years 2005-2009. *Federal Register*. 2006;71(31):8166-8200.

8. Ashe MC. Bone Health Following Spinal Cord Injury. *Spinal Cord Injury Rehabilitation Evidence*. Ed. J. J. Eng et al. 2010. 1-26.

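### Aim 3a counts the incidence of symptoms after infusion with no pre-infusion reading, so arm-specific rates include background illness and a real difference from placebo is diluted

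*Combined protocol and SAP*

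**What the plan says.** Aim 3a (sections B and E.2) hypothesises that, relative to controls, ZA patients will have "an increased incidence of myalgias, fever, gastrointestinal disturbances, and flu-like symptoms over the three days after infusion of study drug". For the analysis, "we will estimate group-specific rates (proportions) along with exact binomial confidence intervals", and "Comparisons between groups will be performed using Fisher's exact test". No rule says whether a symptom present before the infusion counts.

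The design (section D) is a "prospective, double-blind, randomized, placebo-controlled trial with a 2:1 ratio of ZA to placebo in 48 persons with complete traumatic SCI". Symptom assessment first appears under Days 1-7 after infusion: "Subjects will be assessed daily for 3 days, then weekly for one month after study drug administration for known side effects of the drugs". The safety monitoring section repeats that schedule, uses a standardised form, asks about any side effect, and provides for recording adverse events.

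Before infusion, screening covers history, examination, pregnancy test and laboratory values. The baseline visit ("A Baseline Assessment will be completed between 8 and 21 days post-injury, and include the following") lists FRAX, blood samples and DXA. Neither these lists nor Table 4 contains a reading of the 3a symptoms. Section E.1 compares the arms on age, FRAX risk, sex and injury level, not on symptoms. There is a contact just before dosing: "A confirmatory exam will be conducted in the 24 hours prior to study drug delivery".

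**The concern.** Incidence means new events. These patients are at most three weeks from a major injury that the protocol itself describes as inflammatory, and the eligibility criteria do not exclude current fever, muscle pain or bowel symptoms. Unless the interview form asks about onset, a symptom carried over from before dosing is counted like one caused by the drug.

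The arm-specific rates are a stated output, and a reader will take the ZA rate as the reaction rate in acute injury. The efficacy and biomarker models all adjust for a baseline value; Aim 3a has nothing to adjust for. A pre-dose reading that was not taken cannot be recovered later.

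**Working it through.** **Inputs.** From the documents: 48 patients at 2:1, so 32 v 16; Fisher's exact test; significance level 0.05; fever 15% among the known reactions (section C, side effects). Assumed, because the documents give no figures for acute injury: background rate *b* from 0% to 50%, equal in both arms, and a larger drug effect of 30%. The plan gives no expected rate, sample size or power for Aim 3, so there is no figure of its own to reproduce here.

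**Step 1: no drug effect.** Both arms have rate *b*, so the expected difference is 0. Exact enumeration of the two-sided test at 32 v 16, over *b* from 0% to 50%, gives false rejection of at most 3.2% in either direction, and at most 1.6% with ZA looking worse.

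**Step 2: real drug effect *e* among those without background symptoms.** The ZA rate is *b* + (1 − *b*)*e*, the placebo rate is *b*, and the difference is (1 − *b*)*e*.

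| Background *b* | ZA rate, *e* = 15% | Difference, *e* = 15% | Difference, *e* = 30% | Fisher power, *e* = 30% |
|---|---|---|---|---|
| 0% | 15% | 15 points | 30 points | 79% |
| 10% | 23.5% | 13.5 | 27 | 45% |
| 30% | 40.5% | 10.5 | 21 | 21% |
| 50% | 57.5% | 7.5 | 15 | 12% |

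For example, 0.30 + 0.70 × 0.15 = 0.405, and 0.405 − 0.30 = 0.105.

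**Step 3: chance imbalance.** At 30% prevalence before dosing, the standard deviation of the difference between arms is √[0.3 × 0.7 × (1/32 + 1/16)] = √(0.21 × 0.09375) = 0.14, or 14 points. That is about as large as the 15% fever rate.

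**Step 4: three event definitions.** Take *b* = 30%, all present before infusion, with fresh background *n* of 0% to 5% after it. For the new-or-worse count, patients who already have the symptom worsen because of the drug at a rate *w* between *e*/2 and *e*. The event rate is then *n* on placebo and (1 − *b*)[*n* + (1 − *n*)*e*] + *b*[*n* + (1 − *n*)*w*] on ZA. At *e* = 30% the extremes are 30% v 0% (*n* = 0, *w* = *e*) and 29.2% v 5% (*n* = 5%, *w* = *e*/2).

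| Event counted | Power, *e* = 15% | Power, *e* = 30% |
|---|---|---|
| Any symptom after infusion | about 6% | 19-21% |
| New onset only (22 v 11 symptom-free patients) | 1-3% | 29-33% |
| New or worse (all 32 v 16) | about 4-13% | about 46-79% |

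If only half of the 30% background is present before infusion, new-onset counting (all 32 v 16) moves power from 21% to 25% at *e* = 30% and from 6% to 8% at *e* = 15%. The reading cannot remove illness that starts after dosing.

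**The case against.** The strongest objection is that Aim 3a is a blinded, randomised comparison with placebo, assessed on one schedule in both arms. A reader might infer that background illness will be reported as a drug effect. The documents do not support that: step 1 shows no bias under the null, and the error in the test runs towards missing an effect. The placebo rate also stands beside the ZA rate, which warns a careful reader. This part of the objection stands, and it confines the point to the meaning of the arm-specific rates, dilution, and imbalance that cannot be seen.

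Second, counting only new onset lowers power at 15%, the only fever rate the protocol gives. That stands too, and is why worsening must count.

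Third, the interview form is not in the public document and may ask about onset. That is possible, but onset recalled after dosing is weaker than a reading taken before it, and the analysis section states no event rule.

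A reader might also infer that headache and arthralgia, listed among the most common reactions at 6% and 5% but not named in 3a, are lost to the safety evaluation. They are not: the interview covers any side effect, adverse events are recorded, and flu-like symptoms, left undefined, might include them. Their omission has no bearing on background illness. At those rates and zero background, Fisher power would be 0.05% and 0.01%, so testing them would answer nothing.

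**Conclusion.** The point holds in a limited form. Without a pre-infusion reading, Aim 3a cannot deliver an incidence: the arm-specific rates mix prior and new symptoms, a true difference shrinks by the factor (1 − *b*), and chance imbalance is invisible. The comparison with placebo remains valid under no drug effect.

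The size depends on background rates that the documents do not give. At an assumed 30%, a 15% effect shows as 10.5 points inside a ZA rate of 40.5%. At a 15% effect, power is low under every definition. The gain from a reading is therefore in interpretable rates and in detecting larger reactions, and it is smaller if much of the background starts after dosing. This is a secondary tolerability aim with no power claim, but the change is cheap and must be made before dosing.

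**What to change.** - Give the existing standardised interview, with charted temperature, once at the confirmatory exam in the 24 hours before infusion.
- Define a 3a event as a symptom new or worse than that reading. Define worse in advance for each symptom, and keep all randomised patients in the denominator.
- Report the risk difference against placebo with its confidence interval beside the arm-specific rates, and show prior symptoms by arm.
- Headache and arthralgia may be listed descriptively; they need not be tested.

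Cost: a few minutes per patient at a contact that already takes place, one more use of an existing form, and a short definition in the analysis section. The drawback is that the rule for worsening needs care: if it is too strict, the count approaches new onset alone, with the loss of power for small effects shown in step 4.
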